**Figure 1: Study Schematic Diagram**

S – Screening R- randomization

## 1.2 Database Lock

The end of the study is defined as the date of the last safety follow up via phone call of the last participant in the study.

A Blind Data Review Meeting (BDRM) will take place prior to Database Lock (DBL) and Analysis Sets will be agreed.

## 1.3 Study Populations

There are 3 populations of interest. These are as follows:

[figure not shown]
- **Primary Population** : Subjects recruited under the new design, plus those from the original design recruited to SoC2 (not being treated with nintedanib or pirfenidone prior to screening) and randomized to either placebo or 3mg GB0139.
- **SoC1 Population/Combination**: Subjects recruited under the original design to SoC1 (current treatment at baseline with nintedanib or pirfenidone).
- **SoC2 Population/Monotherapy**: Those subjects from the original design in the SoC2 stratum (not receiving nintedanib or pirfenidone at baseline), plus all subjects from

	Plus-Project Statistical Analysis Plan	
	Protocol Number: GALACTIC-1	Version: 1

the new design. SOC2/Monotherapy Population is the Primary Population plus SoC2 10 mg.

These populations are described visually in Figure 2 below.

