6.4 Study Design Rationale

Based on the DSMB's recommendation, GALACTIC-1 can continue to randomise participants with IPF to receive either placebo or 3 mg GB0139 in a randomized and blinded fashion.

A placebo treatment arm included in the study is to allow for a quantitative assessment of the efficacy of 3 mg GB0139 compared with an inactive control. Use of the placebo is also essential in the evaluation of the GB0139 safety in this study.

DSMB also recommended no further co-administration of GB0139 with nintedanib and pirfenidone. Therefore, patients who are not currently taking or cannot tolerate nintedanib or pirfenidone will be eligible for screening (Section 7.0). Furthermore, nintedanib and pirfenidone are defined as study prohibited medications in Protocol version 6.1_UK.

Eligible participants will be randomized in a ratio of 2:1 to receive either 3 mg GB0139 or placebo. The updated design has maintained the ratio of active to placebo in the original study design, after the 10 mg GB0139 treatment group was removed in Protocol version 6.1_UK.

The 12 months (52 weeks) treatment duration is considered optimal for evaluating the primary endpoint in the study.

FVC is generally accepted as a measure of disease severity and as a predictor of survival in IPF. FVC is also commonly used as the primary efficacy measure for clinical trials in IPF. The decline of lung function in IPF is punctuated by acute exacerbations which carry a substantial risk of hospitalization and mortality. Thus, any intervention which reduces the time to exacerbation represents a substantial benefit and will be evaluated. In addition to measurements of lung volume (FVC), diffusion capacity for carbon monoxide (DLCO) as well as oxygen saturation (SpO₂) will be monitored and assessed as secondary lung function endpoints.

Survival is recognised as an important measure to evaluate effect of a potential treatment for IPF therefore, time to death (all-cause mortality) is included as one of the key secondary endpoints. Patients with IPF also suffer from dyspnea, cough and poor exercise tolerance, which can reduce the quality of life and cause a severe restriction in their activities of in every-day life. Therefore, a number of patient-reported outcome instruments including SGRQ will be used to document the effect on symptoms and their impact on the patient's quality of life.

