14.5.2 Safety Analysis

The primary assessment of benefit-risk of GB0139 3 mg compared to Plc will be based on efficacy and safety data over 52 weeks. All safety assessments described below will focus on

data collected within the first 52 weeks of the study. In addition, selected safety analyses will be repeated to include data collected beyond 52 weeks; further details will be specified in the SAP.

All treated subjects will be included in the safety analysis. The primary safety assessment will be based on the participants who received 3mg or placebo as study treatments. A separate safety assessment will be made for the participants who received study treatment in combination of nintedanib or pirfenadone. The particular tables and figures to be split in this way will be specified in the SAP. In general, safety analyses will be descriptive in nature. No hypothesis testing is planned.

Kaplan-Meier plots will be produced for the time to premature treatment discontinuation. Statistical analysis and reporting of adverse events will concentrate on treatment-emergent adverse events. All adverse events occurring between start of treatment and end of the residual effect period will be considered 'treatment-emergent'. The residual effect period is defined as the 28 days after the date of the last dose of trial medication. Adverse events that start before first drug intake and deteriorate under treatment will also be considered 'treatment-emergent'. Frequency, severity, and causal relationship of adverse events will be tabulated by system organ class and preferred term after coding according to the current version of MedDRA.

Laboratory data will be analysed both quantitatively as well as qualitatively. The latter will be done via comparison of laboratory data to their reference ranges. Values outside the reference range as well as values defined as clinically relevant will be highlighted in the listings. Treatment groups will be compared descriptively with regard to distribution parameters as well as with regard to frequency and percentage of subjects with abnormal values or clinically relevant abnormal values.

Vital signs, physical examinations, or other safety-relevant data observed at screening, baseline, during the course of the treatment and at the end-of-treatment evaluation will be assessed with regard to possible changes compared to findings before start of treatment.

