**Figure 2: Populations for analysis**

Randomized treatment and randomization strata will be identified per the randomization schedule post-unblinding.

Unless otherwise stated, all analyses will be conducted in the Primary Population. Analysis will be repeated in the SoC1 / Combination and / or SoC2 / Monotherapy Population where specified. For the SoC1 / Combination and SoC2 / Monotherapy Populations, there is an additional treatment arm and therefore an extra column will be displayed in the corresponding outputs.

A summary table showing the composition of the three populations by population, part and treatment group will be provided.

For further details on selection of subjects for analysis, see Section 4, Analysis Sets.

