#### **4.5 Per Protocol Set (PPS)**

The PPS is a subset of the mITT set consisting of subjects who complied with the protocol sufficiently to ensure that these data would be likely to represent the effects of study intervention according to the underlying scientific model (e.g., subjects with at least 80% treatment compliance as defined in Section 7.3.1). It is used for efficacy sensitivity analyses and will only apply to the Primary Population.

It consists of all randomized and dosed subjects who meet key inclusion/exclusion criteria, only received the treatment they were randomized to, and did not have protocol deviations that were considered to impact efficacy. Subjects recruited under the original study design and who started nintedanib or pirfenidone whilst still on randomized treatment and prior to 52 weeks (i.e., in combination with study treatment) will be excluded from the PP Set. The following list of criteria will be used to exclude subjects from the Primary Population:-

- Not in Primary Population
- HRCT not done
- Treatment compliance not 80-120%
- FVC (%pred)  $\leq 45\%$  at Baseline
- DLCO (corrected for Hb)  $< 30\%$  or  $> 79\%$  of predicted at Baseline
- FEV1/FVC  $< 0.7$  at Baseline
- Use of nintedanib or pirfenidone during study

The final classification of protocol deviations relative to Week 52 will be made during a blinded data review prior to DBL, and all decisions, including exclusions from the PP Analysis Set, will be made blinded to study treatment.

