### 7.1 General Methods and Principles

#### 7.1.1 Analysis of Subgroups

Key subgroups for the study are:-

- Baseline FVC (%PRED): <80%, >=80%
- GAP index: I, II or higher
- Baseline GAL-3 level: < median, >= median\*
- Baseline MMP7: < median, >= median
- Gender (Female, Male)
- SoC treatment at baseline per eCRF (pirfenidone, nintedanib) for SoC1 / Combination Population only. Any SoC1 subject per the randomization who did not receive pirfenidone/nintedanib per the eCRF will be omitted from these subgroup analyses\*\*

\* Median baseline GAL-3 levels will be estimated per SoC population separately.

\*\* Only to be used for FVC (primary endpoint) and treatment compliance.

Other subgroups may be analyzed on inspection of the data.

	Plus-Project Statistical Analysis Plan	
	Protocol Number: GALACTIC-1	Version: 1

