#### **7.3.1 Exposure and Treatment Compliance**

Details of exposure and treatment compliance will be summarized for the mITT Analysis Set, as well as for the Safety Analysis Set. In addition, for the Primary Population only, exposure and compliance will be summarized in the PP Analysis Set.

Date of first dose of study treatment will be derived as the earliest date of drug dispense from the ‘Treatment Compliance’ eCRF forms.

Extent of exposure to GB0139 (mg) or Placebo will be calculated based on information from the ‘Treatment Compliance’ eCRF forms. The number of capsules used will be derived as the number of GB0139 capsules dispensed minus the number of unused GB0139 capsules returned during the study. The number of GB0139 capsules used and the dose of GB0139 in the capsules known to have been dispensed will be used to derive the extent of exposure (mg) to GB0139.

	Plus-Project Statistical Analysis Plan	
	Protocol Number: GALACTIC-1	Version: 1

The duration of exposure to GB0139 in days will be calculated as the date of last dose recorded in the 'Disposition Study Completion' eCRF minus the date of first dispensing of GB0139 + 1.

The duration of exposure to GB0139 will be summarized both as a continuous variable and categorically, with categories 0-13 weeks, >13 weeks – 26 weeks, >26 weeks=39 weeks, >39 weeks – 52 weeks, > 52 weeks.

The extent of exposure (mg) will be summarized as a continuous variable by treatment group.

The extent (mg) and duration of exposure (days) between each dispensing and returning of study drug will be presented in the listings but will not be summarized.

The duration of exposure to nintedanib or pirfenidone during treatment with study drug will be derived based on the start and stop dates of nintedanib and pirfenidone from the 'Pirfenidone/Nintedanib Usage' eCRF and the first and last date of study drug.

The expected treatment exposure (capsules) will be derived using the treatment duration with study drug multiplied by 2 (the planned daily number of capsules).

Treatment compliance based on dispensing data will be derived as 100 x treatment exposure (capsules) / expected treatment exposure for duration of study treatment through study treatment discontinuation (capsules).

The treatment exposure to study drug (capsules), treatment duration with study drug (days) and treatment compliance (continuous and grouped as < 80%, 80% to 120%, > 120%) will be summarized.

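### The SAP sorts safety data into combination and monotherapy by randomisation stratum, whereas the protocol words its separate combination safety assessment by treatment received

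*SAP*

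**What the plan says.** Protocol 14.5.2: "A separate safety assessment will be made for the participants who received study treatment in combination of nintedanib or pirfenadone". It then leaves the choice of outputs to the SAP: "The particular tables and figures to be split in this way will be specified in the SAP".

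SAP 1.3 defines the Combination population as "Subjects recruited under the original design to SoC1 (current treatment at baseline with nintedanib or pirfenidone". The Monotherapy population is the original-design SoC2 stratum plus everyone recruited under the new design. The Primary Population is the same without the SoC2 10 mg arm. Under Figure 2 the SAP adds: "Randomized treatment and randomization strata will be identified per the randomization schedule post-unblinding".

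SAP 7.3 runs safety on the Primary Population and repeats key summaries for the two stratum populations. SAP 7.3.2 does so for serious TEAEs and for TEAEs leading to discontinuation.

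Three other SAP sections recognise that stratum and actual antifibrotic use can differ:

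- SAP 4.5 removes from the Per Protocol Set original-design subjects "who started nintedanib or pirfenidone whilst still on randomized treatment and prior to 52 weeks", and describes this as use combined with study treatment.
- SAP 7.1.1 says: "Any SoC1 subject per the randomization who did not receive pirfenidone/nintedanib per the eCRF will be omitted from these subgroup analyses". That subgroup factor is used only for FVC and treatment compliance.
- SAP 7.3.1 says: "The duration of exposure to nintedanib or pirfenidone during treatment with study drug will be derived", from the start and stop dates on the Pirfenidone/Nintedanib Usage eCRF page.

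**The concern.** The protocol sentence describes an exposure; the SAP population describes a baseline status. The two agree only for subjects whose antifibrotic use on study drug matches their stratum. For anyone else, adverse events are tabulated under a label that does not describe what the subject was taking.

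This matters because co-administration was one of the things the DSMB acted on in February 2021. Protocol 6.4 records: "DSMB also recommended no further co-administration of GB0139 with nintedanib and pirfenidone". A reader of the clinical study report will look to the Combination tables for the safety of that exposure and to the Monotherapy tables for its absence. As planned, neither table isolates it. An event during co-administration in an SoC2 subject would be read as a monotherapy event, and the combination summary would lack it. The effect on the comparison between arms depends on which arm had more starters and on their risk, and neither is known.

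**Working it through.** The point rests on text, so the first step is to set the protocol wording and the SAP tables side by side.

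| Subject | Under the wording of protocol 14.5.2 | Where SAP 1.3 and 7.3 put the events | Agree? |
|---|---|---|---|
| SoC1, antifibrotic taken on study drug | Combination | SoC1/Combination | Yes |
| SoC2 or new design, no antifibrotic on study drug | Not combination | SoC2/Monotherapy; Primary if 3 mg or placebo | Yes |
| Original-design SoC2, antifibrotic started on study drug | Combination | SoC2/Monotherapy; Primary if 3 mg or placebo | No |
| SoC1 stratum, no antifibrotic per eCRF | Not combination | SoC1/Combination | No |
| New design, antifibrotic taken on study drug against the prohibition in protocol 8.3.1 | Combination | SoC2/Monotherapy and Primary | No (deviation only) |

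The second step is to look for a rule that repairs the three mismatches.

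1. SAP 4.4 assigns safety subjects by the first study treatment received. That means GB0139 or placebo, so it does not address the antifibrotic.
2. The SAP 4.5 exclusion applies to the Per Protocol Set. Adverse events are analysed in the Safety Set, so it has no effect there.
3. SAP 7.1.1 covers SoC1 subjects without an antifibrotic, but only in one subgroup factor for FVC and compliance.
4. SAP 7.3.1 derives the overlap of antifibrotic and study drug as an exposure measure. No adverse event, laboratory, ECG or MACE summary uses it.
5. SAP 7.2.5.2 and 7.2.5.3 summarise time to antifibrotic initiation (original-design SoC2) and termination (SoC1), without linking either to events.
6. SAP 4.6 leaves presentation by treatment-received group to the blinded data review meeting and sets no rule for antifibrotic use.

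No safety table is therefore defined by actual co-use, and none ends or reassigns follow-up when an antifibrotic starts.

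The third step is size. The documents do not give the number of on-drug starters or of SoC1 subjects without an antifibrotic, so only an illustration is possible. Let f be the share of a monotherapy-labelled arm with combined exposure, p1 the event risk without it and p2 the risk with it. Then

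labelled risk = (1 − f) × p1 + f × p2.

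All values here are assumptions:

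- p1 = 20%, p2 = 40%: f = 5% gives 19 + 2 = 21%; f = 10% gives 18 + 4 = 22%; f = 20% gives 16 + 8 = 24%.
- p1 = 15%, p2 = 30%: f = 5% gives 14.25 + 1.5 = 15.75%; f = 10% gives 13.5 + 3 = 16.5%; f = 20% gives 12 + 6 = 18%.

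If f were 5% in one arm and 20% in the other, the first pair of risks would produce a difference of 24 − 21 = 3 points in either direction. The formula treats a starter as exposed throughout, so it overstates the effect for someone who started late.

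**The case against.** The strongest reply is that the protocol may use combination as shorthand for SoC1. The opening of protocol Section 14 frames the amended comparison within the SoC2 stratum, and protocol 14.5 also splits by stratum. Stratum is fixed before treatment, so arms within it stay as randomised. Antifibrotic initiation comes after randomisation and may reflect progression. Keeping starters in the tables also matches the primary estimand, which includes FVC after antifibrotic initiation. Since the amendment, co-use is prohibited on study drug, and co-exposed subjects can be identified from the derived exposure and the listings.

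Much of this stands. It supports keeping the tables by stratum as the main presentation, and it limits new cases to deviations. It does not remove the mismatch: the protocol says received, SAP 4.5 uses the idea of combined treatment for SoC2 starters, and identifiability in listings is not a separate assessment. Stopping current users in 2021 does not take their data out either, because SAP 1.3 defines membership by stratum.

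A reader might infer more than the documents support:

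- **That such subjects are known to exist.** SAP 4.5 and 7.1.1 are contingency rules. They show that the cases were foreseen, not that they occurred.
- **That the primary safety comparison was meant to exclude antifibrotic use.** Protocol 14.5.2 defines it by receipt of 3 mg or placebo and adds no such condition.
- **That a count follows from SAP 1.1.** About 320 randomised less about 200 discontinued leaves about 120 continuing. The 200 include current antifibrotic users, so the 120 are the wrong base. The 200 also include 52-week completers; those in SoC2 on 3 mg or placebo remain in the Primary Population, so 120 is no upper limit.
- **That each misassigned event has a known weight.** A 2:1 split of 141 gives 94 and 47, but the Primary Population also contains original-design subjects randomised 1:1 between 3 mg and placebo.
- **That SAP Section 9 conceals a departure.** It lists changes from protocol version 7.0. The protocol text available refers to version 6.1_UK, so the wording of 14.5.2 in version 7.0 cannot be checked.

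**Conclusion.** The mismatch is real and lies in the text: an exposure-worded safety assessment in the protocol, and only stratum-based safety tables in the SAP. Any SoC2 subject who started an antifibrotic on study drug is counted as monotherapy and is absent from the combination assessment. Any SoC1-stratum subject without an antifibrotic is counted as combination. The size and direction of any distortion are unknown; the percentages in the working rest on assumed risks and shares and are not estimates for this trial. The conclusion assumes that protocol 14.5.2 means what it says by received, and that the version the SAP cites has the same wording. It does not show that the stratified tables are invalid. They should be supplemented, because co-administration was a subject of the DSMB's recommendation and the data needed are already collected.

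**What to change.** Keep the tables by stratum as the main presentation and add to SAP 7.3.2 a supplementary descriptive set, by arm, for serious TEAEs, fatal TEAEs and TEAEs leading to discontinuation, with rates per 100 patient-years. Classify by actual co-administration, using the dates on the Pirfenidone/Nintedanib Usage eCRF page:

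- count events and person-time from first co-administration as combination;
- end monotherapy follow-up at that point;
- leave out of the combination group any subject with no antifibrotic while on study drug, including such subjects in the SoC1 stratum.

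Flag the affected subjects in the listings and report their number by arm. State that initiation is a post-randomisation and possibly informative event, so the tables are descriptive and support no test. While editing, correct SAP Section 5, where the labels are reversed (SoC1 is paired with monotherapy and SoC2 with combination).

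The cost is a short addition to the SAP and a few extra tables from dates that SAP 7.3.1 already uses. No new data are needed, and no primary or key secondary analysis changes.
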